#### 8.1.2 Safety Assessment Windowing

For all safety summaries, windowing will be applied to the Week4/Premature Discontinuation Visit and Follow-up Period Visit assessments to ensure safety data from subjects with similar lengths of exposure and/or follow-up are summarized together. Windowing of safety assessment from these visits will be applied as follows:

- Safety assessments will be considered part of the scheduled visit window if they fall within +/- 3 days of the nominal study visit day.
- Safety assessments completed on Days 1-3 will also be windowed to the Week 1 visit.
- Safety assessments completed 3 to 10 days after the last dose of study drug will be windowed to the Week 5/1-Week Follow-up Visit
- Safety assessments completed 11 to 17 days after the last dose of study drug will be windowed to the Week 6/2-Week Follow-up Visit
- In the event of multiple assessments within the same visit window, the assessment closest to the nominal study day will be used. In the event of a tie, the latest study day will be used.

Subjects missing safety assessments at baseline will have the most recent visit value prior to date of first dose used as the baseline value.

Safety assessment listings will include both the reported and windowed visit labels. Any assessment completed outside of the windows for which that particular assessment was scheduled to be completed per the protocol will be labeled as "Unscheduled".

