Abbreviations: AE=adverse event; con med=concomitant medication; CGI-S=clinical global impression-severity; C-SSRS=Columbia-Suicide Severity Rating Scale; ECG=electrocardiogram; MADRS=Montgomery-Asberg Depression Rating Scale; PK=pharmacokinetics; Premature D/C=Premature Discontinuation from treatment; QIDS-SR=Quick Inventory of Depressive Symptomatology – Self Report; Q-LES-Q-SF=Quality of Life Enjoyment and Satisfaction Questionnaire – Short Form; SDS=Sheehan Disability Scale

- ¹ If a clinic visit is not possible (e.g., due to illness), a remote visit may be conducted to complete all assessments that can be done remotely and assess for adverse events and concomitant medications. The Screening, Baseline, and Week 4/Premature Discontinuation Visits cannot be done remotely. The sponsor should be contacted prior to conducting any remote visits whenever possible.
- ² Height and body weight at Visit 1. Body weight only at Visit 2 and Visit 6/Premature Discontinuation.
- ³ Physical examinations will include a review of the following body systems: general appearance, skin and extremities, ear/eyes/nose/throat, head/neck, heart/chest, abdomen, musculoskeletal, and neurological.
- ⁴ Baseline/Screening Version at Visit 1; Since Last Visit Version at Visits 2-8.
- ⁵ All females; Serum pregnancy test at Visit 1 and Visit 6 (or Premature Discontinuation); Urine pregnancy test at Visit 2 – if urine pregnancy test at Visit 2 is positive, a confirmatory serum pregnancy test will be conducted.
- ⁶ Clinical safety labs include clinical chemistry, hematology, coagulation, and urinalysis. Labs should be collected in a fasting state. Urinalysis not required at Visit 4 (Week 2 visit).
- ⁷ Vital signs include blood pressure, pulse rate, and oral body temperature. Vital signs to be assessed in a sitting position after three mins or more of quiet sitting.
- ⁸ Two ECGs to be collected at the Baseline Visit separated by approximately 10 minutes. One ECG collected at all other visits.

TABLE OF CONTENTS

TITLE PAGE	1
INVESTIGATOR'S PROTOCOL AGREEMENT PAGE	2
SPONSOR EMERGENCY CONTACT INFORMATION.....	3
PROTOCOL SYNOPSIS	4
SCHEDULE OF EVENTS	12
TABLE OF CONTENTS.....	14
1. LIST OF ABBREVIATIONS AND DEFINITIONS OF TERMS.....	21
2. INTRODUCTION	25
2.1. Major Depressive Disorder.....	25
2.2. Investigational Product	25
2.2.2. Non-clinical Studies.....	26
2.2.3. Clinical Studies.....	27
2.2.3.1. SP-624-101	27
2.2.3.2. SP-624-102	28
2.3. SP-624 Development Plan.....	29

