9.3.9.5. C-SSRS

Frequency and severity of suicidal ideation and suicidal behavior as measured by the C-SSRS will be summarized by treatment for each visit.

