#### 8.3.7.6 C-SSRS

Two summary tables will be prepared by treatment group for the C-SSRS assessment

- 1. Summary of C-SSRS (Baseline/Screening Version) at Screen
- 2. Summary of C-SSRS (Since the Last Visit Version) by Visit

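### The SAP 8.1.2 closest-to-nominal rule can leave a Since Last Visit C-SSRS form, and any ideation it records, out of the only post-baseline C-SSRS table listed

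*SAP*

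**What the plan says.** SAP 8.1.2 opens with its scope: "For all safety summaries, windowing will be applied to the Week4/Premature Discontinuation Visit and Follow-up Period Visit assessments". It then sets the windows: "Safety assessments will be considered part of the scheduled visit window if they fall within +/- 3 days of the nominal study visit day", and, for follow-up, "Safety assessments completed 3 to 10 days after the last dose of study drug will be windowed to the Week 5/1-Week Follow-up Visit". Where a window holds more than one assessment, "In the event of multiple assessments within the same visit window, the assessment closest to the nominal study day will be used"; ties are broken in favour of the later day.

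SAP 8.3.7 lists the C-SSRS among the safety evaluations, and neither 8.1.2 nor 8.3.7.6 exempts it. Footnote 4 to the protocol's Schedule of Events (Table 2) specifies the form: "Since Last Visit Version at Visits 2-8".

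SAP 8.3.7.6 plans one table for the screening version and one for later visits: "Summary of C-SSRS (Since the Last Visit Version) by Visit" (Table 14.3.2.7.2). Under SAP 8.3.7.1, unscheduled and repeat safety assessments are listed but not tabulated. Protocol 9.3.9.5 asks for this: "Frequency and severity of suicidal ideation and suicidal behavior as measured by the C-SSRS will be summarized by treatment for each visit".

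**The concern.** Keeping the value nearest the nominal day is reasonable for a blood pressure or a laboratory result, because two readings a few days apart are near-substitutes. Two Since Last Visit forms are not. Each asks about ideation, attempts and preparatory acts since the previous visit, so the retained form does not repeat what the other records.

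The discontinuation visit is the natural source of a second form in a window. It falls on whatever day the subject stops, and Protocol 5.4 asks sites to make every attempt to complete it. What is at stake is the completeness of the by-arm suicidality summary in a depression trial. The SAP already uses worst-value logic elsewhere: 8.3.7.3 plans categorical tables of maximum QTcF and of maximum and minimum heart rate. Nothing similar is planned for the C-SSRS.

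**Working it through.** The documents give no figure for this point, so there is none to reproduce. The check applies the 8.1.2 rule to every day combination that the schedule permits.

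**Inputs**
- Treatment windows: nominal day ±3, so Days 4–10, 11–17, 18–24 and 25–31 (SAP 8.1.2). Days 1–3 also go to Week 1 but are not used here.
- Week 5 window: 3 to 10 days after last dose (SAP 8.1.2), with nominal day +7 (SAP Table 6.1).
- Week 5 visit: 4 to 10 days after the discontinuation visit (Protocol 7.1).
- Selection: smallest distance from nominal; ties go to the later day.
- Assumption: a visit 0–2 days after last dose is placed by study day, and one 3 or more days after by the follow-up rule. 8.1.2 does not say which rule governs when a day meets both.

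**Example.** The Week 2 visit is on Day 13, with no ideation. The discontinuation visit is on Day 17, with the subject dosed that day and ideation recorded. Both lie in Days 11–17. The distances from Day 14 are |13 − 14| = 1 and |17 − 14| = 3. Day 13 is kept, and the ideation does not appear in Table 14.3.2.7.2.

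**A. Discontinuation visit in the same window as the preceding scheduled visit (Weeks 1, 2 or 3).** Let a be the scheduled visit's offset from nominal and b the discontinuation visit's offset, with −3 ≤ a < b ≤ 3. There are 7 × 6 / 2 = 21 pairs for each week. The discontinuation form is dropped when |b| > |a|:
- b = +1: a = 0, giving 1 pair
- b = +2: a = −1 to +1, giving 3 pairs
- b = +3: a = −2 to +2, giving 5 pairs
- b ≤ 0: none

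The discontinuation form is dropped in 1 + 3 + 5 = 9 pairs. The earlier form is dropped in 21 − 9 = 12, of which 3 are ties. One form is dropped in all 21.

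**B. Discontinuation visit p ≥ 3 days after last dose, with the Week 5 visit also in the +3 to +10 window.**
- p = 3 (distance 4): Week 5 at +7, +8, +9 or +10 (distances 0–3); discontinuation form dropped in 4 of 4
- p = 4 (distance 3): Week 5 at +8, +9 or +10 (distances 1, 2, 3; the tie goes to the later); dropped in 3 of 3
- p = 5 (distance 2): Week 5 at +9 (tie, dropped) or +10 (kept); dropped in 1 of 2
- p = 6 (distance 1): Week 5 at +10 (distance 3); dropped in 0 of 1

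The discontinuation form is dropped in 4 + 3 + 1 + 0 = 8 of 10 pairs, and the Week 5 form in 2.

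**After the fix.** Combining all forms in a window drops none of the 21 pairs in A and none of the 10 in B.

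**The case against.** The best case for the plan has five parts.

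- **Nothing is destroyed.** A reader might infer that the event is lost or its only record deleted. It is not: Listing 16.3.5.2 covers the Since Last Visit responses, and safety listings show both reported and windowed visit labels. This stands, but a listing gives no count by arm.
- **AE tables are a second route.** Protocol 7.2.5.7 contemplates suicidal ideation and behavior reported as AEs, and AE tables use no visit windows. This stands in part. Protocol 8.1.4 keeps events considered symptoms of MDD out of the AE data, so the backup is incomplete, especially for ideation.
- **The scope is narrow.** The opening sentence of 8.1.2 limits windowing to Week 4/Premature Discontinuation and follow-up assessments. A reader might suppose that every routine visit is exposed. The text does not support that, although the discontinuation visits in A and B fall squarely inside the stated scope.
- **The protocol promises only a by-visit summary.** The SAP supplies one, so an any-time row would be an addition and its absence breaks no commitment.
- **The shells are not available.** SAP 11 puts them in a separate document. An overall row inside Table 14.3.2.7.2 cannot be excluded, although neither its title nor 8.3.7.6 suggests one.

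**Conclusion.** The concern holds as a gap in one table. Followed literally, SAP 8.1.2 can remove a positive Since Last Visit form from the only post-baseline C-SSRS table listed, on schedules that the protocol allows. Unscheduled and repeat forms are left out of the table by a separate rule in 8.3.7.1. The summary is descriptive, so no formal test is affected.

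The size is a count of possible schedules: one form dropped in 21 of 21 pairs in A (9 discontinuation, 12 earlier) and in 10 of 10 in B (8 discontinuation, 2 Week 5). Case B rests on the stated assumption about which window rule governs.

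A reader might turn 9 of 21 into a loss rate of 43%. That would require all day pairs to be equally likely, and it would apply only to visits that share a window. Suppose instead that scheduled visits are spread evenly over ±3 days and discontinuation visits evenly over Days 8–28. Then 3 × (1 + 3 + 5)/7 = 27/7 of 21 days, or 18.4% of discontinuation visits, would lose their form. Neither assumption comes from the documents, and either would count forms, not positive forms. The 20–30% dropout in Protocol 9.3.5 and SAP 8.3.5.5 is a general figure for MDD studies and does not say who attends a discontinuation visit or when. The actual frequency, and any difference between arms, therefore cannot be computed. Nor do the documents show that suicidality is recorded more often at discontinuation visits.

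**What to change.** - In SAP 8.1.2 and 8.3.7.6, exempt the C-SSRS Since Last Visit version from the closest-to-nominal rule. For each window, report the most severe ideation category and any suicidal behavior across all forms in it. The windows keep their purpose of grouping subjects with similar exposure or follow-up.
- Add to Table 14.3.2.7.2, for each arm, a row for any ideation after first dose (by worst category) and any behavior, using all post-dose forms including unscheduled ones. SAP 8.3.7.1 then needs a matching exception for unscheduled and repeat C-SSRS forms.

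The cost is a few sentences in the SAP and minor programming on data already collected; no study procedure changes. The one downside is a possibly slightly less favourable count.

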5.4. Subject Withdrawal from the Study

A subject may be withdrawn from the study at any time at the discretion of the Investigator.

Justifiable reasons to discontinue a subject from the study may include, but are not limited to, safety, ability or willingness to comply with conditions of the protocol, withdrawal of consent, lost to follow-up, Investigator discretion, Sponsor decision, or premature termination of the study.

The reason(s) for premature discontinuation will be documented on the subject's CRF.

Any AEs or SAEs that lead to study discontinuation should be followed as appropriate until the AE has resolved or stabilized (in the opinion of the Investigator and Sponsor Medical Monitor).

Subjects who prematurely discontinue after receiving a dose of study drug, should continue to be followed for scheduled safety assessments according to the SOE ([Table 2](#)), if possible. At a minimum, every attempt should be made to complete the Week 4 / Premature Discontinuation procedures; however, subjects are free to withdraw consent from participation in the study at any time, without prejudice to their medical care.

If a subject is lost to follow-up (i.e., fails to return for study visits), all reasonable efforts should be made to contact the subject and complete the Week 4 / Premature Discontinuation procedures.

Should it be discovered after a subject has begun study treatment that the subject did not meet all inclusion and exclusion criteria, or if during the study a subject ceases to meet all inclusion and exclusion criteria, the subject's continued participation in the study will be discussed with the Medical Monitor.

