#### 8.3.7.1 Safety Analyses

All summaries of safety and tolerability will be performed on the safety population.

Laboratory parameters, vital sign data, and ECG results will be summarized by treatment group and presented in tabular and graphic formats where appropriate. Appropriate change from Baseline calculations for the mean change from baseline within each treatment group where appropriate will be used for laboratory parameters, vital sign values, ECG results, and C-SSRS results, but no formal statistical tests are planned.

Form STAT401.V3 Page 15 of 23

Client/Project	Arrivo/Sirtsei 201
Version and Date	V01 August 26, 2022

Shift tables will also be provided for laboratory parameters.

Unscheduled and Repeat safety assessments will be listed but will not be summarized in the tabular summaries. Local laboratory results will be listed but will not be summarized in the tabular summaries.

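### SAP 8.1.2 with 8.3.7.1 drops protocol-required discontinuation-visit labs (Days 1-10 and 18-24), urinalysis and weight (before Day 25) from the safety tables

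*SAP*

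**What the plan says.** SAP 8.1.2 sets the windowing for every safety summary: "windowing will be applied to the Week4/Premature Discontinuation Visit and Follow-up Period Visit assessments". Its stated aim is to group subjects with similar exposure or follow-up. The rules are:

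- "Safety assessments will be considered part of the scheduled visit window if they fall within +/- 3 days of the nominal study visit day".
- Results from the first three days of dosing are added to Week 1.
- "Safety assessments completed 3 to 10 days after the last dose of study drug will be windowed to the Week 5/1-Week Follow-up Visit".
- Any assessment "outside of the windows for which that particular assessment was scheduled to be completed per the protocol will be labeled as" 'Unscheduled'.

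SAP 8.3.7.1 then gives that label its consequence: "Unscheduled and Repeat safety assessments will be listed but will not be summarized in the tabular summaries".

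In the Schedule of Events (Protocol Table 2), the post-baseline safety labs fall at Week 2, Week 4/PD and Week 5. Footnote 6 waives urinalysis at Week 2. For weight, footnote 2 reads "Body weight only at Visit 2 and Visit 6/Premature Discontinuation". Protocol 5.4 makes the PD visit the minimum sought from anyone who stops early: "every attempt should be made to complete the Week 4 / Premature Discontinuation procedures".

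**The concern.** The protocol has one column for Week 4 and PD, so labs, urinalysis and weight are required at a PD visit whenever it happens. The SAP splits that column by study day and tests each result against the schedule of the week in which it lands. A PD lab on Day 8 or Day 20 lands in a week with no labs, so a required result is treated like a discretionary one.

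This looks like an oversight. Adding Days 1-3 to Week 1 shows that the authors wanted very early PD data summarized. That works for assessments done every week and fails for those done less often.

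Safety and tolerability are a secondary objective, and prior repeated dosing at 20 mg is five subjects for 10 days (Protocol 2.2.3.2). Lab summaries, shift tables and the weight table are where a between-arm pattern could show without depending on an investigator's judgement of clinical significance. They would be thinnest for subjects who stopped early.

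**Working it through.** The plan gives no figure of its own on this point, so the check is a day count.

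**Inputs**
- Nominal visit days 7, 14, 21 and 28, the 3-day margin and the Days 1-3 rule: SAP 8.1.2 and Protocol Table 2. Days count from first dose (SAP 8.1.3).
- Assessments due at each visit: Protocol Table 2 and footnotes.
- Dropout 20-30% (SAP 8.3.5.5): 0.2 x 300 = 60 to 0.3 x 300 = 90 subjects.
- 'On drug' means a PD visit at most 2 days after the last dose. This is an assumption. SAP 8.1.2 only starts the Week 5 window at 3 days; the explicit 2-day rule is in 8.1.1, for efficacy.

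**Step 1: windows.** Week 1 is Days 4-10 plus Days 1-3, so Days 1-10 (10 days). Week 2 is Days 11-17 (7 days), Week 3 is Days 18-24 (7 days) and Week 4 is Days 25-31. Days before the Week 4 window: 10 + 7 + 7 = 24.

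**Step 2: is the assessment scheduled in the window where the PD visit lands?**

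| Assessment | Week 1 | Week 2 | Week 3 | Days relabelled |
|---|---|---|---|---|
| Blood labs | no | yes | no | 10 + 7 = 17 of 24 (70.8%) |
| Urinalysis | no | not required | no | 24 of 24 |
| Weight | no | no | no | 24 of 24 |
| ECG, vital signs, physical exam, C-SSRS | yes | yes | yes | 0 of 24 |

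The blood-volume table (Protocol Table 6) agrees on labs: only the 6 mL PK sample at Week 1 and nothing at Week 3. Labs on Days 11-17 do reach the Week 2 row, unless another sample closer to Day 14 displaces them.

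**Step 3: PD visits 3-10 days after the last dose.** These go to Week 5. Labs and urinalysis are scheduled there and are tabulated, but as off-drug values: SAP Table 8.1 takes the drug as cleared after 3 days. Weight is not scheduled at Week 5, so it is relabelled again.

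**Step 4: from days to subjects.** The documents give no distribution of leaving days. Let p be the share of on-drug PD visits before Day 25 that fall on Days 11-17. The share of PD lab sets lost is 1 - p.

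| Split: Days 1-10 / 11-17 / 18-24 | Lab sets lost |
|---|---|
| Even over 24 days | 1 - 7/24 = 70.8% |
| Equal thirds | 67% |
| 50/30/20% | 70% |
| 20/30/50% | 70% |
| 25/50/25% | 50% |
| All on Days 11-17 | 0% |
| All on Days 1-10 | 100% |

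With even spread and every leaver attending on drug before Day 25, the lab sets lost are 60 x 17/24 = 42.5 to 90 x 17/24 = 63.75. Urinalysis and weight lose 60 to 90 values each. These are upper bounds for even spread. If only 30-80% attend on drug (an assumed range with no source in the documents), the lab figure is 60 x 0.3 x 17/24 = 12.75 to 90 x 0.8 x 17/24 = 51.

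**Step 5: who has no on-drug lab in any table?** Mainly leavers on Days 1-10: 10/24 = 41.7% under even spread, or 60 x 10/24 = 25 to 90 x 10/24 = 37.5 subjects. Leavers on Days 18-24 lose the PD sample but normally keep their Week 2 lab.

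**Step 6: is the value recovered elsewhere?** The list of tables in SAP 10.1 has lab summaries, shift tables and a vital signs and weight table. No title names an end-of-treatment or last-on-treatment summary.

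**The case against.** **'Unscheduled' may mean something else.** The label is defined in a paragraph about listings. SAP 8.3.7.1 pairs the word with repeat tests, much as Protocol 7.1 speaks of discretionary unscheduled or repeated assessments. On that reading PD labs stay in the tables. It is possible but weaker: 8.1.2 defines the word as the windowed label, and its windowing governs all safety summaries. If the other meaning is intended, the same edit settles it.

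**The values are not lost to safety reporting.** This stands. Every result is listed with both visit labels. Clinically significant abnormalities become adverse events (Protocol 8.1.1), and events leading to withdrawal have their own table. Protocol 5.4 also asks that early leavers continue scheduled safety visits. What these do not replace is the descriptive comparison of values between arms.

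**The table shells are in a separate document.** A PD row could exist there. The SAP text does not provide for one.

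**Stronger readings.** A reader might infer that most early leavers' safety data never reach a table. The documents do not support that: ECG, vital signs and C-SSRS are scheduled weekly and are tabulated, physical exams are listed by design, and 'most' for blood labs depends on unknown leaving days. A reader might also infer that the rule biases the safety conclusion toward a clean result. That is not shown either. The rule is the same in both arms, the quoted dropout is all-cause, and no document says how much of it is intolerance.

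**Conclusion.** The point holds for blood labs, urinalysis and weight. As written, the SAP leaves required on-drug PD results out of the lab, shift and weight tables. For labs this happens on 17 of 24 possible days. For urinalysis and weight it happens on all 24, if the Week 2 urinalysis waiver is read as not scheduled; otherwise urinalysis follows the labs at 17 of 24. PD weight taken 3-10 days after the last dose is excluded as well.

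The day counts follow from the text once 'on drug' is taken as within 2 days of the last dose. Any percentage or number of subjects rests on assumed leaving days and attendance. Because the loss is confined to descriptive tables, this is a should-fix item, and it does not touch the primary analysis.

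One related gap: SAP 8.1.3 numbers days after the last dose as +1 and +2 and windows on that number. It is therefore unclear where a PD visit 1-2 days after the last dose belongs.

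**What to change.** - In SAP 8.1.2, state that protocol-required assessments from the Week 4/Premature Discontinuation visit do not count as 'Unscheduled' for the purposes of 8.3.7.1.
- Keep the by-visit rows as they are. Add a separate 'Premature Discontinuation' or 'last on-treatment value' row (last value within 2 days of the last dose, PD included) to the lab, urinalysis, shift and weight tables. Using the last on-treatment value would bring coverage of on-drug PD visits from 7 to 24 of 24 days for labs, and from 0 to 24 of 24 for urinalysis and weight.
- State how visits 1-2 days after the last dose are windowed.
- Do not move PD values to the nearest window in which the test is scheduled. A Day 3 weight would then sit in the Week 4 row, which defeats the purpose of the windowing.

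The cost is SAP wording and one extra row per table, with no new data. The added row mixes exposure lengths, so it should stand beside the by-visit rows and not replace them.
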